two drugs – exenatide (BID) and liraglutide (QD) are administered subcutaneously. They have been demonstrated to improve glycemic control in this population and, in some individuals, lead to sustained weight loss.

This study aims to determine whether acute exposure to liraglutide decreases the mean weekly blood glucose levels in adolescents with T1DM. In addition, we will determine whether liraglutide decreases glucose excursions following a meal challenge. *The overall hypothesis to be tested is that short-term exposure (7 days) to liraglutide improves glycemic control in adolescents/young adults with T1DM treated with continuous subcutaneous insulin infusion.*

**Specific Aim 1:** Determine whether liraglutide decreases the mean weekly blood glucose levels in adolescents/young adults with T1DM. *Hypothesis: Mean weekly blood glucose will decrease when liraglutide is used as an adjuvant therapy to insulin in individuals with T1DM.* Subjects will wear continuous glucose monitors to measure interstitial glucose as a surrogate for blood glucose. The CGM will be worn for 7 days pre- and post- daily liraglutide treatment. Data will be downloaded and mean weekly blood sugars will be determined.

**Specific Aim 2:** Determine whether liraglutide treatment decreases blood glucose excursion during mixed meal tolerance test in adolescents/young adults with T1DM. *Hypothesis: Post-prandial blood glucose excursions are attenuated with liraglutide treatment.* Mixed meal tolerance tests will be performed with and without pre-treatment with liraglutide. Blood glucose levels will be measured at set time points during the test and blood glucose excursions as well as blood glucose AUC in response to the meal challenge will be calculated.

**Specific Aim 3:** Determine whether glucagon secretion decreases during mixed meal tolerance test in subjects treated with liraglutide. *Hypothesis: Glucagon secretion following a meal challenge is suppressed in response to liraglutide treatment.* Serum samples will be drawn during mixed meal tolerance test performed with and without pre-treatment with liraglutide. Glucagon will be measured by ELISA and glucagon secretion AUC will be calculated.

**Specific Aim 4:** Determine whether liraglutide treatment leads to a reduction in total daily insulin dose.

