*Hypothesis: Improved glycemic control can be attained with lower total daily insulin requirements in subjects treated with liraglutide.* Total daily insulin dose will be determined for seven days before and after initiation of liraglutide therapy. Insulin dose/kilogram body weight will be determined and evaluated in relationship to changes in mean weekly blood sugars.

In addition to the specific aims outlined above, the following exploratory aims will be addressed:

**Exploratory Aim 1:** Determine the side effect profile of liraglutide in adolescents/young adults with T1DM. *Hypothesis: Side effect profile of short-term liraglutide treatment in this population will be similar to that reported in adults.* Study subjects will keep a diary reporting hypoglycemic events and other potential adverse effects. Type, number, and rate of adverse events will be determined.

**Exploratory Aim 2:** Determine if there is a difference in caloric intake with liraglutide treatment in adolescents/young adults with T1DM. *Hypothesis: Caloric intake decreases in response to liraglutide treatment.* Subjects will keep a 4 day food record before and after initiation of liraglutide. Total caloric intake will be calculated, and within subject differences in caloric intake before and after liraglutide treatment will be determined.

**Exploratory Aim 3:** Determine if liraglutide treatment alters serum inflammatory markers in subjects with T1DM. *Hypothesis: Acute liraglutide therapy decreases serum levels of C-reactive protein and increases adiponectin levels in subjects with T1DM.* Serum samples before and after liraglutide therapy will be drawn and levels of inflammatory markers will be measured. Within subject differences will be determined.

Describe any relevant preliminary data.

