## 7.0 Study Endpoints

7.1 *Describe the primary and secondary study endpoints.*

Response: For statistical purposes, the **primary endpoint** of the study is to detect a difference between untreated and treated periods in the change from baseline in mean weekly blood glucose concentrations. The statistical analysis will be carried out using

analysis of variance (ANOVA) and tested at the 0.05 level. The results will be computed as mean $\pm$ SD.

The secondary end points based on glycemic changes will include the difference from baseline in standard deviations of the mean weekly glucose concentrations, mean fasting blood glucose concentrations, the duration of time spent in hyperglycemia ( $>150\text{mg/dl}$ ,  $>200\text{mg/dl}$ ,  $>250\text{mg/dl}$ ) and hypoglycemia ( $<70\text{mg/dl}$ ,  $<40\text{mg/dl}$ ), and insulin dosage. A reduction in the area under curve following the meal will constitute another secondary end point. Within subject comparisons of the magnitude of change from baseline will also be made for these glycemia related secondary endpoints using student's t-test. Comparisons for these and the primary endpoints will also be made using the paired *t*-test or Wilcoxon's test for paired data for each subject. Additional secondary end-points of the study will be change from baseline in 1) mean weekly blood glucose 2) glucagon area under the curve concentrations following meal challenge 3) change in daily insulin dose (total dose and units/kg) 4) caloric intake based on 4 day food records and 5) change in serum adiponectin and CRP levels before and after initiation of liraglutide treatment. The relation between change in postprandial sugars, glucagon, and total daily insulin dose will be studied by regression analysis to evaluate the relative contribution of each of these parameters to the improvement in post-prandial blood sugars.

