#### **Visit 3**

- Insulin pump settings
- Total daily insulin dose
- Food diaries
- Download of continuous glucose monitor – mean weekly blood sugars
- Blood sugar records with reports of hypoglycemia
- Adverse effects
- Mean blood glucose excursion, glucagon release, and serum inflammatory markers during mixed meal tolerance test

*Describe any primary or secondary safety endpoints.*

**Response:** Adverse effects including nausea/vomiting, anorexia. Injection site reactions/pain. Rates of hypoglycemia. Clinical or biochemical evidence of pancreatitis.

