## **8.0 Procedures Involved**

### *8.1 Describe and explain the study design.*

**Response:** This is a pilot unblinded prospective within subject investigational-drug intervention trial.

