#### **Visit 1 Screening Day (day 0):**

- Review the subject's medical history and family medical history
- Review subject's blood sugars and insulin pump settings
- Measure height, weight, blood pressure and heart rate.
- The principal investigator will perform a physical exam.
- If hemoglobin A1c level is not recorded in the medical record within 2 weeks of visit 1, this test will be performed.
- Record mean total daily insulin dose (previous 72 hours) from insulin pump.
- Subjects will be advised to wear his/her continuous glucose monitor (CGM) for the next two weeks, changing sites as indicated by the manufacturer.
- For subjects who do not have a CGM, we will insert the Abbott Freestyle Libre Professional Device. This device will monitor glucose levels throughout the entire study period. Subjects will be advised to check blood sugars at least 4 times per day and at any occasion when symptoms of hypoglycemia develop.
- Subjects will be asked to keep a record of any episodes of hypoglycemia.
- Subjects will be asked to keep a 4 day food record (three days, 1 weekend day).
- Subjects will be advised to follow their usual diabetes care plan with respect to carbohydrate counting, diet and exercise.

**Visit 2 (Day 7):** Subjects will come fasting for this visit. They will bring the food records and diary of hypoglycemia to this visit. This visit will take approximately 4 hours. At this visit, the following procedures will be performed:

- Records of blood sugars and CGM data will be obtained from subjects wearing personal CGMs
- Subjects wearing the Freestyle LibrePro system will continue wearing the device unless it became dislodged during the study. A new device will be placed in this case.
- Blood sugars and insulin pump settings will be reviewed.
- Record mean total daily insulin dose (previous 72 hours) from insulin pump.
- A Mixed Meal Tolerance test will be performed (see below)

- Insulin pump settings will be adjusted to decrease the risk of hypoglycemia during liraglutide treatment. Basal rates will be decreased by 25% and meal boluses will be decreased by 33%.
- The first dose of liraglutide will be given at the study site. Subjects will be given 0.6 mg subcutaneously. Subjects will be taught how to use the delivery device at this visit.
- Subjects will be advised to take 0.6 mg of liraglutide subcutaneously every morning at about the same time.

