- Subjects will be given a diary and be asked to record any episodes of hypoglycemia, as well as any other side effects such as nausea, decrease in appetite, and other problems.
- Subjects will be asked to keep a 4 day food record (three days, 1 weekend day).
- Subjects will be provided with contact information for the principal investigator in case of any problem or untoward side effect. They will be asked to notify the study staff for persistent low blood sugar (BS < 70 mg/dL), persistent high blood sugar (BS > 250 mg/dL), or urine ketones.
- Subjects will be advised to return to clinic in 7 days.

**Visit 3 (Day 14):** This is the final study visit. Subjects will come fasting for this visit. The subject will not take liraglutide prior to coming to this visit but will bring the study drug to the visit. Subjects will bring the food records and diary of hypoglycemia to this visit. This visit will take approximately 4 hours. At this visit, the following procedures will be performed:

- Records of blood sugars and CGM data will be obtained.
- Freestyle LibrePro device will be removed and data obtained.
- Blood sugars and insulin pump settings will be reviewed
- Record mean total daily insulin dose (previous 72 hours) from insulin pump.
- Liraglutide (0.6 mg subcutaneously) will be administered 45 minutes prior to the Mixed Meal Tolerance Test
- A Mixed Meal Tolerance test will be performed (see below).
- All study drug will be returned.
- Subjects will be advised to resume previous basal rates and carbohydrate ratios within 48 hours of final study visit.

**Mixed Meal Tolerance Test (MMTT).** This test will be done at Visit 2 and Visit 3. The MMTT is a test to measure blood sugar levels in response to a meal and the amount of glucagon that is produced in response to changes in blood sugar. Prior to the test, a catheter will be placed to reduce the number of needle sticks during the test. Subjects will drink 240 ml of a high protein nutrition drink (BOOST). An appropriate amount of insulin for the carbohydrate intake of the meal challenge will be administered via insulin pump to taking the drink. Blood will drawn once before the meal and 8 times during the meal over 3 hours. The total amount of blood that will be drawn is ~ 20 teaspoons (100 mL).

The following parameters will be drawn for measurement during the MMTT

- Blood Glucose
- Glucagon
- Serum inflammatory mediators

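### The protocol lowers pump insulin as liraglutide starts, so a fall in daily insulin dose (Aim 4) cannot by itself be credited to the drug

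*Combined protocol and SAP*

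**What the plan says.** Specific Aim 4 (section 1.3) is worded causally: "Determine whether liraglutide treatment leads to a reduction in total daily insulin dose". Its text adds that "Total daily insulin dose will be determined for seven days before and after initiation of liraglutide therapy", and that "Insulin dose/kilogram body weight will be determined and evaluated in relationship to changes in mean weekly blood sugars".

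Section 8.1 describes the design: "This is a pilot unblinded prospective within subject investigational-drug intervention trial". Each subject has an untreated week followed by a treated week, and there is no control group.

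Section 8.2, Visit 2, sets the insulin reduction at the same visit as the first liraglutide dose: "Basal rates will be decreased by 25% and meal boluses will be decreased by 33" percent. Section 13.1 repeats the 25% for basal but gives 30% for carbohydrate boluses. Subjects return to their earlier settings only after Visit 3. Section 13.1 allows insulin to be raised again during the week, and section 8.2 asks subjects to call for persistent low glucose and for "persistent high blood sugar (BS > 250 mg/dL), or urine ketones". No adjustment algorithm is given.

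Sections 7.1 and 10.1 list insulin dose among the secondary endpoints and list its change again as total dose and units/kg. On testing they say: "Within subject comparisons of the magnitude of change from baseline will also be made for these glycemia related secondary endpoints", by t-test, with a paired t-test or Wilcoxon test as well. Daily dose also enters a regression meant to apportion the improvement in post-meal glucose.

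**The concern.** The quantity that Aim 4 tests is one that the protocol itself changes at the moment treatment begins. The pre-treatment dose is measured before the cut and, by default, the post-treatment dose is measured under it. No group or period has the cut without liraglutide, and no reference value represents the cut. A test against zero therefore asks whether dose changed at all, not whether liraglutide changed insulin need.

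A significant fall could be reported as a drug effect when some or all of it was imposed by protocol. Section 14.1 says the results may be used to develop longer randomized, placebo-controlled studies, so a misattributed effect could carry forward.

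For glucose (Aims 1 and 2) the direction is opposite. Section 13.1 itself expects a risk of hyperglycemia from the reduced insulin. The cut could mask or shrink a glucose benefit, but it would not explain an observed fall.

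**Working it through.** **The plan's own figure.** Section 10.2 gives a change of 22 mg/dL, SD 20 mg/dL, 80% power, alpha 0.05 and a paired t-test, hence 9 subjects. With d = 22/20 = 1.10 and the noncentral t distribution (two-sided), power is 76.1% at n = 8 and 82.3% at n = 9. The figure of 9 reproduces; at the planned maximum of 12, power is 93.3%. The sample size is not at fault, but it concerns mean glucose and not insulin dose.

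**Imposed fall in daily dose.** Let b be the basal share of daily insulin (not given in the documents). If settings are kept and all bolus insulin is cut:

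- imposed fall (%) = 25b + 33(1 − b) with the section 8.2 figure, or 25b + 30(1 − b) with the section 13.1 figure;
- b = 1 gives 25%; b = 0 gives 33% or 30%;
- b = 0.5 gives 12.5 + 16.5 = 29.0%, or 12.5 + 15.0 = 27.5%.

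Correction boluses may not be covered by the cut. If 50% of the dose is basal, 30% is meal bolus and 20% is uncut correction insulin, the 30% figure gives 0.5 × 25 + 0.3 × 30 = 21.5%.

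**Chance of a significant result with no drug effect.** This is the two-sided paired t-test at 0.05, with noncentrality √n × (net fall / SD). The SD of the within-subject percent change is not in the documents, so a range is shown. How much of the cut would be undone is also unknown. For n = 9:

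| Scenario | Net fall | SD 10 | SD 15 | SD 20 | SD 30 |
|---|---|---|---|---|---|
| 29% cut kept | 29% | 1.00 | 0.999 | 0.966 | 0.720 |
| Half undone | 14.5% | 0.966 | 0.720 | 0.481 | 0.249 |
| 75% undone | 7.25% | 0.481 | 0.249 | 0.161 | 0.098 |
| 21.5% cut, 75% undone | 5.375% | 0.296 | 0.158 | 0.110 | 0.076 |
| 90% undone | 2.9% | 0.120 | 0.081 | 0.067 | 0.058 |
| Fully restored | 0% | 0.05 | 0.05 | 0.05 | 0.05 |

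For n = 12, at SD 10 / 20 / 30: kept 1.00 / 0.995 / 0.861; half undone 0.995 / 0.629 / 0.334; 75% undone 0.629 / 0.209 / 0.119.

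The top row is an upper end. If the drug did nothing, glucose would be expected to rise and insulin to be raised again.

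**Uneven undoing.** The table tests percent change and holds the SD constant. As a check, I simulated the change in absolute units with n = 9, an assumed log-SD of 0.35 for daily dose, and the share undone varying uniformly from 0 to 100% across subjects (half on average). For SD 10 to 20 points, rejection is 0.38 to 0.78 instead of 0.48 to 0.97. With the cut kept it is 0.94 to 1.00.

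**Dose window.** Aim 4 uses seven days before and after the start; the visit procedures record the previous 72 hours. The last 72 hours of the treated week come after any upward changes made earlier in it. A seven-day mean includes the first days, when the imposed cut is most fully in force. The two windows can therefore give different answers on the same subjects.

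**The case against.** The strongest reply is that Aim 4's hypothesis is joint: better control at a lower insulin requirement, with dose per kilogram read against the glucose change. Lowering insulin and seeing whether glucose still improves is a coherent test of that, and a lower dose with worse glucose would not support it. This is fair as a reading of section 1.3. But sections 7.1 and 10.1 list dose change as an endpoint of its own, with its own test and no joint rule, so the intention does not reach the analysis.

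A second reply is that insulin can be raised and that section 8.5 already collects basal dose, total dose and the basal/bolus split from pump downloads. Both are true. Raising insulin shrinks the false signal, but unless the cut is fully reversed the final dose mixes the imposed cut, later adjustment and any drug effect. The downloads would help to describe this, but no analysis uses them to separate the parts.

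Third, the probabilities depend on assumed SDs and shares undone, and uneven undoing lowers the middle rows somewhat. That stands, and it is why a range is given. The imposed cut itself needs no assumption.

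Finally, this is one secondary aim of an unblinded pilot, and the cut works against the drug on the primary glucose endpoint. That limits the consequence but does not make the separate dose test interpretable.

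**Conclusion.** The concern holds. As analysed, a significant fall in daily insulin dose cannot by itself be credited to liraglutide, because the protocol imposes a fall and the test uses zero as its reference. If settings are kept and all bolus insulin is cut, the imposed fall lies between 25% and 33% for any basal share. The resulting false-attribution rate runs from near certainty when the cut is kept (0.97 to 1.00 at n = 9, SD 10 to 20 points) to the nominal 0.05 when it is fully undone. Where the trial would fall in that range depends on the basal share, the SD and the extent of later increases, none of which the documents give.

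A lower dose together with lower glucose would be more informative, since the cut does not explain a glucose fall. What would then remain is the general limit of an uncontrolled before/after comparison. The primary endpoint's sample size is unaffected. This should be fixed before analysis.

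**What to change.** 1. In sections 7.1 and 10.1, stop using the test of insulin dose against zero as evidence that liraglutide reduces insulin need. Report the change (total and units/kg) descriptively with a 95% CI, state the protocol-imposed reduction, and list later setting changes. Interpret it only jointly with the change in mean weekly glucose and its 95% CI.
2. Treat the regression on the relative contribution of daily dose as descriptive.
3. Record the insulin units and bolus ratio used at each meal test. "Insulin pump settings" are already among the variables at every visit, but the ratio used for the meal test is not stated, and the Visit 3 test runs on reduced basal rates unless they were raised during the week. Describe the size of the glucose effects in Aims 1 and 2 as liraglutide plus the protocol insulin reduction versus usual insulin.
4. Reconcile the two bolus figures (33% in section 8.2, 30% in section 13.1). State which dose window, seven days or 72 hours, defines the endpoint, and apply it to both periods.

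The cost is wording in sections 7.1 and 10.1, the reconciliation in item 4, and two extra entries at two meal tests per subject. No visit, sample or device is added. Aim 4's claim becomes narrower: it describes dose and glucose together and no longer offers the dose fall alone as a liraglutide effect.

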## **11.0 Provisions to Monitor the Data and Ensure the Safety of Subjects**

*11.1 Describe the plan to periodically evaluate the data collected regarding both harms and benefits to determine whether subjects remain safe.*

Response: [name] is responsible for review of data on a regular basis to ensure that collected data is being entered correctly. All unforeseen events during the study tasks will be reported immediately to the principal investigator; if necessary, they will be reported to the IRB.

*11.2 Describe what data are reviewed, including safety data, untoward events, and efficacy data.*

Response: Data related to study tasks will be reviewed.

*11.3 Describe how the safety information will be collected (e.g., with case report forms, at study visits, by telephone calls with participants).*

Response: Safety information will be documented on the data collection tool as necessary.

*11.4 Describe the frequency of data collection, including when safety data collection starts.*

Response: [name] is responsible for collection and review of all data.

*11.5 Describe who will review the data.*

Response: [name]

*11.6 Describe the frequency or periodicity of review of cumulative data.*

Response: see above

*11.7 Describe the statistical tests for analyzing the safety data to determine whether harm is occurring.*

Response: Number of severe hypoglycemic events will be documented. The rate of severe hypoglycemia will be compared to historical data.

*11.8 Describe any conditions that trigger an immediate suspension of the research.*

Response: Episode of pancreatitis.

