Glucagon-like peptide 1 is an incretin hormone that is released in response to ingestion of food. Long-acting GLP-1 analogues and drugs which inhibit the metabolism of GLP-1 are FDA-approved as adjuvant therapy for the treatment of Type 2 diabetes. These drugs are currently not approved for use in the T1DM population. Individuals treated with GLP-1 analogues are at increased risk for hypoglycemia. It is recommended that patients treated with insulin secretagogue therapies (ie sulfonylureas), have their secretagogue dose decrease when GLP-1 analogue therapy is initiated. In this study, subjects have T1DM and are reliant on insulin for blood sugar control. In order to decrease the risk of hypoglycemia in this population, subjects will be counseled to decrease their basal insulin rates by 25% and their bolus insulin coverage for carbohydrates by 30% during the seven days when they are receiving liraglutide. All study subjects will be advised to check their blood sugar if they experience any symptoms consistent with hypoglycemia. They will be asked to contact the study team for persistent hypoglycemia while taking liraglutide. In addition, because insulin doses will be decrease significantly when liraglutide is initiated, there is the risk that subjects will experience hyperglycemia and may develop ketonuria. Subjects will be advised to contact the study team for persistent hyperglycemia and/or presence of urine ketones. The insulin dose will be increased to address this concern.

The most common side effects experienced by adults taking liraglutide include headache, nausea, and diarrhea. Nausea is most common when first starting liraglutide but generally decreases with time. Subjects may also feel less hungry while taking liraglutide. We will monitor for these and additional side effects during the study.

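### Headache and diarrhea, listed among the commonest adult side effects, are not named in the diary instruction or safety endpoints, and 12 subjects cannot support a claim of similarity to adults

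*Combined protocol and SAP*

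**What the plan says.** Section 13.1 (Risks to Subjects) states: "The most common side effects experienced by adults taking liraglutide include headache, nausea, and diarrhea". It adds that subjects may feel less hungry, and closes the paragraph with a commitment: "We will monitor for these and additional side effects during the study".

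Section 8.2, Visit 2, is where the side-effect diary is handed out. Subjects are to record episodes of hypoglycemia, "as well as any other side effects such as nausea, decrease in appetite, and other problems". At Visit 1, for the untreated week, they are asked to record hypoglycemia only.

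The safety endpoints at the end of section 7.1 read: "Adverse effects including nausea/vomiting, anorexia. Injection site reactions/pain. Rates of hypoglycemia". Evidence of pancreatitis follows.

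Exploratory Aim 1 (section 1.3) carries the hypothesis: "Side effect profile of short-term liraglutide treatment in this population will be similar to that reported in adults". The planned summary is: "Type, number, and rate of adverse events will be determined". No adult rate, margin or test is given. The only external safety comparison in the analysis text is in section 11.7: "The rate of severe hypoglycemia will be compared to historical data".

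Section 10.2 sets the sample size at 9, enrolling up to 12, on the glucose endpoint alone.

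**The concern.** Two matters meet in Exploratory Aim 1.

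The first is recording. The protocol expects three common symptoms and names one of them, nausea, where subjects are told what to write down. Headache and diarrhea depend on the subject deciding that they count as another problem. Vomiting and injection-site reactions are named as endpoints but not in the diary instruction. Symptoms that are named tend to be recorded more readily than symptoms that are not, so the profile could lean toward the named ones for reasons unrelated to the drug. With no general symptom record in the untreated week, a symptom with a background rate, such as headache, also has no within-subject baseline.

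The second is inference. A hypothesis of similarity is a claim of no important difference. It needs a reference rate, a margin and enough subjects, and the plan has none of these. Section 14.1 says the results may be used to develop longer randomized trials. A low count of headache or diarrhea could be carried forward as reassurance that the data cannot give.

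**Working it through.** **1. What is named where**

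| Symptom | Expected (13.1) | Diary instruction (8.2, Visit 2) | Safety endpoint (7.1) |
|---|---|---|---|
| Nausea | named | named | named |
| Reduced appetite | named | named | named, as anorexia |
| Headache | named | not named | not named |
| Diarrhea | named | not named | not named |
| Vomiting | not named | not named | named |
| Injection-site reaction | not named | not named | named |

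The lists in 8.2 and 7.1 are introduced by open wording, so a symptom not named is still within scope.

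**2. The plan's own sample size**

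Inputs from 10.2: change 22 mg/dL, SD 20 mg/dL (read as the SD of the within-subject change), 80% power, alpha 0.05, paired t-test. The standardized effect is 22/20 = 1.1, and at n = 9 the noncentrality is 1.1 × √9 = 3.3. Two-sided exact power is 76.1% at n = 8 and 82.3% at n = 9. The stated 9 reproduces; at n = 12 power is 93.3%. None of this concerns side effects.

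**3. Precision for a side effect**

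Exact (Clopper-Pearson) limits for x of n are the 2.5% quantile of Beta(x, n−x+1) and the 97.5% quantile of Beta(x+1, n−x).

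| Observed | Exact 95% interval |
|---|---|
| 0/12 | 0 to 26.5% |
| 1/12 | 0.2 to 38.5% |
| 3/12 | 5.5 to 57.2% |
| 4/12 | 9.9 to 65.1% |
| 0/9 | 0 to 33.6% |

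The chance of seeing no event is (1−p)^12: for p = 10% it is 0.90^12 = 28%, and for p = 20% it is 0.80^12 = 7%.

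**4. Could 12 subjects show similarity?**

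The documents give neither adult rates nor a margin, so both are assumed over a range. The criterion is that the 90% exact interval lies wholly within the adult rate ± margin, with the true rate equal to the adult rate.

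| Assumed adult rate | Power, ±10 points | ±20 points | ±30 points |
|---|---|---|---|
| 5% | 0% | 54% | 88% |
| 10% | 0% | 28% | 66% |
| 20% | 0% | 28% | 56% |
| 30% | 0% | 0% | 49% |
| 40% | 0% | 0% | 44% |

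Only a 5% adult rate with a ±30-point margin passes 80%, and that margin would accept a rate of 35%. The smallest n reaching 80% at ±20 points is 28, 36 and 44 for adult rates of 10%, 20% and 30%; at ±10 points it is 82, 142 and 181.

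A non-significant difference would not help either. Against a fixed adult rate (exact test, two-sided 5%), power at n = 12 is 51% for a true 30% against 10%, and 33.5% for a true 40% against 20%.

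**5. Illustration of under-recording**

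These inputs are assumptions. With a true incidence of 25%, 12 × 0.25 = 3 subjects are expected. If a fraction r of unprompted events is written down, the recorded number is 3r: 1.5 at r = 0.5, 2.25 at 0.75 and 2.7 at 0.9. For a true 20% event, the chance of recording none rises from 7% to (1 − 0.20 × 0.5)^12 = 28% at r = 0.5, or 9% at r = 0.9.

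**The case against.** The strongest reply is that the protocol already covers these events. Section 13.1 commits to monitoring them, section 8.3 says subjects will be told of potential adverse events, section 7.1 lists adverse effects without restriction as a Visit 3 variable, and section 1.3 describes a diary for other potential adverse effects. A reader might infer that headache and diarrhea are left out of safety monitoring. The documents do not support that: both lists are open and neither event is excluded. The diary form is an attachment that cannot be seen, and it may already name them. What stands is that the written instruction and the endpoint list do not carry through what 13.1 promises.

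A reader might also infer that the comparison with adults is biased. That is not shown. The aim is exploratory, in an unblinded pilot, with descriptive counts and no test. The documents do not say how the adult data were collected, and the recall fractions above are assumed. Under-recording is a plausible risk of unknown size, and at r = 0.5 to 0.9 it is small beside the sampling uncertainty. If the adult reports were volunteered, a checklist here could make the two sets less comparable. That objection stands and belongs in the fix.

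Finally, section 12 allows withdrawal for significant side effects, with the data left out of the analysis and the subject replaced. That could remove events from the profile more directly than diary wording does. It is a separate matter that this point does not resolve.

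**Conclusion.** The point holds as a limited one. The diary instruction and the safety endpoints name some expected symptoms and omit two that the protocol itself lists as common in adults. This creates a risk of uneven recording, with a plausible direction and an unknown size.

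The hypothesis of similarity to adults cannot be supported by this trial. Exact 95% intervals at n = 12 are about 26 to 58 points wide, and for assumed adult rates of 10% to 40% no margin up to ±30 points gives more than 66% power. The interval widths need only the enrollment ceiling of 12; the power figures rest on the assumed rates and margins. The primary glucose endpoint and its sample size are unaffected.

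**What to change.** - **Section 8.2, diary.** Use one fixed daily yes/no list: nausea, vomiting, reduced appetite, headache, diarrhea, abdominal pain, injection-site reaction, other. If the attached form already has such a list, say so in 8.2.
- **Section 8.2, Visit 1.** Have subjects complete the general symptoms on the same list in the untreated week, alongside the hypoglycemia record, to give a within-subject baseline.
- **Section 7.1.** Name headache and diarrhea among the safety endpoints.
- **Section 1.3, Exploratory Aim 1, and section 10.1.** Replace the similarity hypothesis with a descriptive statement, for example: *For each listed symptom and each week in which it is collected, we will report the number and proportion of subjects with at least one event and the exact 95% confidence interval. No conclusion of similarity to adults will be drawn.*

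The cost is one revised diary page, completed for a further week, and a few sentences of protocol text, with no change to visits or sample size. The downside is that a prompted list will record more events and may be less comparable with adult data if those were volunteered; the report should say so. The similarity claim is given up.
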